## Tables and Descriptive Statistics

All data will be summarized by study part, dose group, day, and/or nominal time point, as appropriate. Data for subjects who received placebo will be pooled across dosing cohorts belonging to the same trial part. Repeated and unscheduled measurements included in the listings will not be used for statistical analyses or summaries, unless the repeated measurement was performed due to unreliable values/technical reasons, eg, clotted samples.

# Presentation of Continuous and Qualitative Variables for Demographics, Other Baseline Characteristics, and Safety

Continuous variables will be summarized using descriptive statistics, ie:

- number of subjects, number of subjects with non-missing values
- mean, standard deviation (SD)
- median, 25th Percentile 75th Percentile (Q1-Q3)
- minimum (Min) and maximum (Max).

Qualitative variables will be summarized by counts and percentages.

Unless otherwise stated, the calculation of proportions will be based on the number of subjects in the analysis set of interest. Therefore, counts of missing observations will be included in the denominator and presented as a separate category.

When the analysis refers only to certain visits, percentages will be based on the number of subjects still present in the study at that visit, unless otherwise specified.

Mean, Median, Q1, Q3, Min, and Max will have the same precision as collected for SDTM datasets for non-derived data. Standard deviation will be presented with one digit more than the mean. Statistics on derived data will be rounded to reasonable digits whereas maximal digits should be

available in Analysis Data Model (ADaM) datasets. Percentage and percent change from baseline will be reported using 1 decimal digit, if not otherwise specified.

### Definition of Baseline

If not otherwise specified, "Baseline" refers to the last scheduled measurement before the IMP administration, as appropriate. However, if a subject is missing the baseline collection, the previous non-missing evaluation (as applicable) will become the baseline value. Baseline of laboratory parameters will correspond to Day 1 predose for Part A, and Day -1 for Part C. Baseline will correspond to Day 1 predose for all parts of the study for vital signs and safety ECGs. Baseline of biomarkers will correspond to Day -1 for Part A,

### Common Calculations

For quantitative measurements:

Change from baseline will be calculated as: Test Value at Visit X – Baseline Value

Age [years]: ([date of informed consent - date of birth] +1)/365.25

### Definition of Duration

Duration in days will be calculated by the difference of start and stop date + 1 if not otherwise specified.

### Handling of Missing Data

Unless otherwise specified, missing data will not be replaced.

Handling of missing data for PK parameter calculations are discussed under Section 16.1.

### Software

Pharmacokinetic parameters will be derived using the validated computer program Phoenix® WinNonlin® 6.4 or higher, and/or SAS® (Statistical Analysis System, SAS-Institute, Cary, North Carolina, USA) Windows Version 9.4 or higher. Pharmacodynamic parameters (excluding those calculated by PK/PD modeling; see Section 16.2.3) will be derived using SAS®. Pharmacokinetic and PD tables, figures, and listings for the final analysis will be developed using SAS®. All other statistical analyses will be performed using SAS®.

# 10 Study Subjects

The subsections in this section include specifications for reporting subject disposition and treatment/study discontinuations. Additionally, procedures for reporting protocol deviations are provided.

### 10.1 **Disposition of Subjects and Discontinuations**

A summary table describing the number and percentage of subjects (as applicable) in each of the following disposition categories will be produced by dose and overall:

- Total number of enrolled subjects (ie, subjects who gave informed consent)
- Number of subjects who discontinued from the study prior to randomization (as applicable), with the reason of discontinuation
- Number of randomized subjects
- Number of randomized subjects who did not receive dose (as applicable)
- Number of treated subjects (used as denominator for percentage calculation for the categories below)
- Number of treated subjects who completed the study
- Number of treated subjects who discontinued the study, with the reason of discontinuation

Corresponding individual listings for study termination status, study entry (including screening failures), and randomization will be prepared. Discontinued subjects will be listed with their reason of withdrawal

Summary of the number and percentage (as applicable) of subjects included in each analysis set (as described in Section 8.2) will be presented.

#### 10.2 Protocol Deviations

#### 10.2.1 Important Protocol Deviations

A listing of important protocol deviations will be provided.

Any PK concentrations which are erroneous due to a protocol violation (as defined in the Clinical Study Protocol), documented handling error, or analytical error (as documented in the bioanalytical report) may be excluded from the PK analysis if agreed upon prior to performing any statistical analyses. In this case, the rationale for exclusion must be provided in the CSR. Any PK concentrations excluded from the PK analysis set will be listed and flagged. Any other PK concentrations that appear implausible to the Pharmacokineticist/PKPD Data Analyst must not be excluded from the analysis. Any implausible data will be documented in the CSR.

#### Reasons Leading to the Exclusion from an Analysis Set 10.2.2

If subjects are excluded from the PK Analysis Set and/or PD Analysis Set, the reasons for exclusion will be listed.

#### **Demographics and Other Baseline Characteristics** 11

Demographics and baseline characteristics will be presented for the Safety Analysis Set.

# 11.1 Demographics

Descriptive statistics will be presented for age, height, weight, and body mass index (BMI). Frequency counts and percentages will be presented for sex, race, ethnicity, and skin type. The summary will be performed by dose and overall.

# 11.2 Medical History

Medical history will be coded using the Medical Dictionary for Regulatory Activities (MedDRA), Version 20.1, and listed.

### 11.3 Other Baseline Characteristics

Other baseline measurements, such as virus screen, alcohol and drugs of abuse screen, pregnancy test and follicle-stimulating hormone assessment in women, nicotine and alcohol consumption, will be listed.

In addition, glucose-6-phosphate dehydrogenase status will be listed for Part C.

### 12 Previous or Concomitant Medications/Procedures

### 12.1 Previous or Concomitant Medications

Medications will be presented for the Safety Analysis Set.

Previous medications are defined as any medication discontinued prior to the IMP administration. Concomitant medications are defined as any medication taken during the course of the study, with a starting date greater than or equal to the IMP administration, or with a starting date prior to the IMP administration and ongoing at the time of the IMP administration.

The Enhanced World Health Organization Drug dictionary (WHO DDE), Version SEP2017, will be used for coding of prior and concomitant medications and they will be described using Preferred Term (PT) as applicable.

Previous and concomitant medications will be listed. Concomitant procedures, if any, will also be listed.

### 12.2 Rescue Medication

Subjects in Part C will be prescribed an approved regimen for curative therapy for malaria, to assure final parasite clearance, at recrudescence or at the end of the study.

Rescue medication data will be listed by subject, including day after inoculum administration.

### 12.3 Intravenous Malaria Inoculum

Intravenous (IV) inoculum will be administered at Day -8 in Part C. Data will be provided in a listing.

#### 13 Treatment Compliance and Exposure

The IMP will be administered at the study site under supervision. The administration of IMP will be listed.

#### 14 Efficacy Analyses

There are no efficacy endpoints defined for Part A.

For Part C, parasitical effect of M5717 will be analyzed as specified in Section 16.2. The malaria clinical score will be analyzed as described in Section 15.2.3.

#### 15 Safety Analyses

The subsections in this section include specifications for summarizing safety endpoints that are common across clinical studies such as AEs, laboratory tests and vital signs.

All safety analyses will be performed for the Safety Analysis Set and will be presented by part and dose. An additional column for all active doses of M5717 may be presented when specified.

#### 15.1 Adverse Events

All AEs recorded during the course of the study will be coded with the MedDRA, Version 20.1, and assigned to a System Organ Class (SOC) and a PT.

Treatment-emergent AEs (TEAEs) are those events with onset dates on or after the first IMP administration. Any AE occurring before the IMP administration on Day 1 and resolved before IMP administration or not worsening after IMP administration will be included in the AE listings, but will not be included in the summary tables (unless otherwise stated). These will be referred to as "pre-treatment" AEs.

In case AE-related dates are partial, the available information will be used in a conservative approach to determine whether the AE is treatment-emergent.

All analyses described in this section will be based on TEAEs if not otherwise specified.

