7.4.1.2 Methods of Recording and Assessing Adverse Events

At each trial visit, the subject will be queried on changes in his or her condition. During the reporting period, any unfavorable changes in the subject's condition will be recorded as AEs, whether reported by the subject or observed by the Investigator.

Complete, accurate, and consistent data on all AEs experienced for the duration of the reporting period (defined below) will be reported on an ongoing basis in the appropriate section of the eCRF. Among these AEs, all SAEs and all nonserious AESIs must be additionally documented and reported using a Serious Adverse Event Report Form as described in Section 7.4.1.4.

It is important that each AE report include a description of the event, its duration (onset and resolution dates [and times, when it is important to assess the time of AE onset relative to the recorded treatment administration time]), its severity (according to the QTS as described in the “Toxicity Grading Scale for Healthy Adult and Adolescent Volunteers Enrolled in Preventive Vaccine Clinical Trials”), its causal relationship with the IMP or rescue medication, any other potential causal factors, any treatment given or other action taken (including dose modification or discontinuation of the IMP), and its outcome. In addition, serious cases should be identified and the appropriate seriousness criteria documented.

Specific guidance can be found in the eCRF Completion and Monitoring Conventions provided by the CRO in coordination with of the Sponsor.

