7.4.1.3 Definition of the Adverse Event Reporting Period

The AE reporting period for safety surveillance begins when the subject is initially included in any part (Part A, B, or C) of the trial (date of first signature of informed consent/date of first signature of first informed consent) and continues until the End of Trial visit (Day 44 ± 2 days) for the subject.

7.4.1.4 Procedure for Reporting Serious Adverse Events, Adverse Events of Special Interest and Dose Limiting Toxicities

Serious Adverse Events

In the event of any new SAE occurring during the reporting period, the Investigator must immediately (within a maximum of 24 HOURS after becoming aware of the event) inform the Sponsors, both Funding and the Local Sponsor, or their designee by fax or by e-mail. All written reports should be transmitted using the SAE Report Form, which must be completed by the Investigator following specific completion instructions.

When an SAE (or follow-up information) is reported by telephone, a written report must be sent immediately thereafter by fax or e-mail. Reporting procedures and timelines are the same for any new follow-up information on a previously reported SAE.

Names, addresses, telephone-, and fax numbers for SAE reporting will be included in the trial-specific SAE Report Form.

All written reports should be transmitted with the SAE Report Form, which must be completed by the Investigator following specific completion instructions.

Relevant pages from the eCRF may be provided in parallel (for example, medical history, concomitant drugs). Additional documents may be provided by the Investigator, if available (for

example, laboratory results, hospital report, autopsy report). In all cases, the information provided on the SAE Report Form must be consistent with the data on the event that are recorded in the corresponding section of the eCRF.

The Investigator must respond to any request for follow-up information (for example, additional information, outcome, final evaluation, other records where needed) or to any question the Sponsors/designees may have on the AE within the same timelines as those noted above for initial reports. This is necessary to ensure prompt assessment of the event by the Sponsor or designee and (as applicable) to allow the Sponsors to meet strict regulatory timelines associated with expedited safety reporting obligations.

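### SAP 15.1 leaves an adverse event that starts before dosing and worsens afterwards neither treatment-emergent nor pre-treatment, so it can drop out of every TEAE table

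*SAP*

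**What the plan says.** SAP 15.1 (Adverse Events) sets the classification in three steps.

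- The TEAE definition: "Treatment-emergent AEs (TEAEs) are those events with onset dates on or after the first IMP administration".
- The pre-treatment category: "Any AE occurring before the IMP administration on Day 1 and resolved before IMP administration or not worsening after IMP administration". Such an event goes into the listings but not, unless otherwise stated, into the summary tables.
- A rule for incomplete dates: "In case AE-related dates are partial, the available information will be used in a conservative approach to determine whether the AE is treatment-emergent".

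The section then makes everything depend on the definition: "All analyses described in this section will be based on TEAEs if not otherwise specified". That covers the overview, SOC/PT, worst-grade, IMP-related and AESI tables in SAP 15.1.1, and the listing in SAP 15.1.2 of events leading to discontinuation.

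On data collection, protocol 7.4.1.2 asks for onset and resolution dates in each AE report, but for "times, when it is important to assess the time of AE onset relative to the recorded treatment administration time" only. Protocol 7.4.1.3 reads: "The AE reporting period for safety surveillance begins when the subject is initially included in any part", which it dates from signed consent. SAP 12.3 adds: "Intravenous (IV) inoculum will be administered at Day -8 in Part C".

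**The concern.** The pre-treatment sentence shows that worsening was meant to matter, yet the TEAE sentence does not mention it. Because the section's analyses rest on TEAEs, a pre-dose event that worsens after M5717 could go uncounted in the tables.

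Part C is where this is most plausible. Subjects are infected before they are dosed, and AEs are collected throughout that interval. Protocol 3.3.3 lists mild to moderate malaria symptoms and transient ALT rises among the possible consequences of the challenge. Protocol 5.2.4 lets the investigator time dosing by symptoms as well as by parasitemia. Nature, incidence and severity of AEs is a Part C secondary endpoint (protocol 8.3.2). The same definition also governs the Part A primary safety endpoint.

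The secondary point is the word dates in the TEAE sentence. The pre-treatment sentence works relative to the moment of administration. The two can disagree on events that start on Day 1 before the dose.

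**Working it through.** The plan gives no figure to reproduce, so the check sets the two sentences side by side over every combination of onset and course.

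**Inputs.** Both rules come from SAP 15.1. The Part C cohort size is 8, with up to 3 cohorts (protocol 5.2.4).

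**Rules.**
- T-date: TEAE if the onset date is on or after the dosing date.
- T-time: TEAE if the onset date and time are at or after dosing.
- P: pre-treatment if onset is before dosing and the event either resolved before dosing or did not worsen after it. For the comparison, an event that is not pre-treatment under P is taken to be a TEAE. The SAP implies this but does not state it.

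| Onset | Course | T-date | T-time | P |
|---|---|---|---|---|
| Before Day 1 | Resolved before dose | Not TEAE | Not TEAE | Pre-treatment |
| Before Day 1 | Ongoing, not worse | Not TEAE | Not TEAE | Pre-treatment |
| Before Day 1 | Worse after dose | Not TEAE | Not TEAE | Not pre-treatment |
| Day 1, pre-dose | Resolved before dose | TEAE | Not TEAE | Pre-treatment |
| Day 1, pre-dose | Ongoing, not worse | TEAE | Not TEAE | Pre-treatment |
| Day 1, pre-dose | Worse after dose | TEAE | Not TEAE | Not pre-treatment |
| After dose | Any | TEAE | TEAE | Not pre-treatment |

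**Results.**
- T-date against P: 3 of 7 rows conflict. One is onset before Day 1 with worsening, which the TEAE sentence omits. The other two are Day 1 pre-dose onsets that resolve or do not worsen, which the TEAE sentence includes and P excludes.
- T-time against P: 2 of 7 rows conflict. Both are pre-dose onset with worsening, and both are omissions by the TEAE sentence.
- Onset before Day 1 with worsening conflicts under either reading.

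**Size per subject.** In one Part C cohort, 1/8 = 12.5 percentage points. Over three cohorts, 1/(3 × 8) = 1/24 = 4.2 points.

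**Not derivable.** The documents give no frequency of symptoms at dosing or of worsening afterwards, so no expected count can be calculated.

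**Missing clock time.** The conservative rule in SAP 15.1 covers partial dates. A complete Day 1 date without a time is not clearly a partial date, so the SAP has no stated default for it.

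**The case against.** The strongest defence is that the pre-treatment sentence already answers the question. It excludes pre-dose events only when they resolve or do not worsen, and that condition has a purpose only if worsened events are to be tabulated. Protocol 7.4.1.2 also has unfavourable changes in a subject's condition recorded as AEs. A worsening may therefore be entered as a new event with a post-dose onset, which the TEAE sentence would capture. In addition, AEs remain in the listings. The malaria clinical score, laboratory values and vital signs are summarised separately without a TEAE filter (SAP 15.2.3, 15.3, 15.4). The analysis is descriptive.

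Much of this limits the consequence, but it does not close the gap. The implied reading may well be the intended one, but the definition to be programmed does not say it. Neither document states whether a worsening is a new AE.

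A reader might infer more: that Part C malaria symptoms present at dosing are misclassified in both directions, and that Day 1 pre-dose events in Part A are counted as treatment-emergent. The documents do not support this. The pre-treatment sentence expressly keeps Day 1 pre-dose events out of the summary tables when they resolve or do not worsen. Over-counting arises only if the TEAE sentence is programmed by calendar date and the next sentence is ignored. Symptoms that begin before Day 1 and do not worsen are pre-treatment under both sentences. Nor would a post-dose worsening in Part C show harm from M5717: that part is open-label without placebo, so the infection itself may be progressing.

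**Conclusion.** The inconsistency is real but narrow. As written, the TEAE definition does not cover a pre-dose AE that worsens after dosing, and the next sentence does not make it pre-treatment either. Programming the stated definition would omit it from all TEAE tables. This holds whether onset is compared by date or by date and time, except that a strict date comparison does pick up worsened events that began on Day 1.

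The consequence is possible under-counting, mainly in Part C, at 12.5 points per affected subject in a cohort of 8. It rests on two assumptions: that such events occur, and that sites record a worsening within the existing AE and not as a new one. The documents settle neither. The Day 1 date-versus-time inconsistency is secondary and depends on a date-only comparison. The correction is worth making because it is cheap and bears on a Part C secondary endpoint.

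**What to change.** In SAP 15.1, replace the TEAE sentence with one rule: a TEAE is an AE with onset date and time at or after first IMP administration, or an AE with earlier onset whose severity grade increases after IMP administration. All other AEs are pre-treatment.

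Add two sentences:
- Day 1 onsets are compared with dosing by clock time. A Day 1 onset with no recorded time is treated as treatment-emergent, as the conservative default.
- State whether a worsening is recorded as a new AE or as a grade change within the existing one, so that the same worsening is not counted twice or missed.

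Each of the seven rows above then has a single classification. Ask the site to record onset time for all Day 1 AEs, since protocol 7.4.1.2 requires it only conditionally. If data collection is complete, query the missing Day 1 times before database lock.

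The cost is a few sentences in the SAP, a line of programming and a short eCRF completion instruction. No new assessments are needed.

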6.3 Assignment to Treatment Groups

Subjects will receive their subject identification number (screening number) as soon as they have signed informed consent. For each cohort in Part A and Part B, subjects who meet all the inclusion criteria and none of the exclusion criteria will be randomized in a double-blind fashion to M5717 or placebo in a ratio of 6:2 (Sentinel 1:1 and Remainder 5:1, or Sentinel 2:1 and Remainder 4:1, based on the SMC decision), respectively. The Investigator or designee will allocate a randomization number (created as per the Sponsor's standards) to each subject in sequential order, immediately before the first administration of the IMP (see Section 8.2). The randomization schedules and individual code-break envelopes (for emergency unblinding, see Section 6.11) for Part A and Part B will be created by a randomization Statistician. For each cohort in Part C, eligible subjects will receive the same M5717 dose with no need for randomization.

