# 8.2 Definition of Analysis Sets and Subgroups

For purposes of analysis, the following populations are defined:

|                       | ,  |  |  |
|-----------------------|--|--|--|
| Population            | Description  |  |  |
| Enrolled              | The Enrolled Analysis Set will include all subjects who provided signed informed consent, regardless of treatment status in the study. This set will be used for subject disposition.  |  |  |
| Safety (SAF)          | The Safety Analysis Set will include all subjects who receive investigational medicinal product (M5717 or placebo for Part A; M5717 for Part C). Subjects will be analyzed according to the actual treatment they receive.   |  |  |
| Pharmacokinetics (PK) | The Pharmacokinetic Analysis Set will consist of all subjects who receive M5717, have no clinically important protocol deviations or important events affecting PK, and provide at least one (measurable) postdose concentration. Subjects will be analyzed according to the actual treatment they receive. All PK analyses will be based on this analysis set. Subjects who receive placebo will not be part of the Pharmacokinetic Analysis Set. |  |  |
| Pharmacodynamics (PD) | The Pharmacodynamic Analysis Set will be defined for Part C only. The Pharmacodynamic Analysis Set will include all subjects who receive M5717 in Part C without clinically important protocol deviations or important events affecting PD. Subjects in the Pharmacodynamic Analysis Set must have evaluable postdose PD data. All PD analyses will be based on this analysis set.   |  |  |

With respect to the use of the analysis sets in the different analyses, it could be presented in a table such as the following:

| Analyses                       | Enrolled
Analysis Set | Safety
Analysis Set | PK Analysis
Set | PD Analysis
Set |
|--------------------------------|--------------------------|------------------------|--------------------|--------------------|
| Subject Disposition            | ✓                        |                        |                    |                    |
| Baseline Assessments           |                          | ✓                      |                    |                    |
| Past and Concomitant Therapies |                          | ✓                      |                    |                    |
| Compliance and Exposure        |                          | ✓                      |                    |                    |

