#### 15.1.1 All Adverse Events

Treatment-emergent AEs will be summarized by dose and overall in tables with:

 The number and percentage of subjects with any TEAE, any IMP-related TEAE, any serious TEAE, any IMP-related serious TEAE, any Grade ≥3 TEAE, any IMP-related Grade ≥3 TEAE, any AEs of special interest (AESI), any TEAE leading to death, any IMP-related TEAE leading to death, any TEAE leading to study discontinuation

- The number and percentage of subjects with at least one TEAE by SOC and PT
- The number and percentage of subjects with at least one TEAE by worst grade, SOC, and PT
- The number and percentage of subjects with at least one IMP-related TEAE by SOC and PT
- The number and percentage of subjects with at least one TEAE by PT only, sorted in decreasing incidence overall
- The number and percentage of subjects with non-serious TEAEs by SOC and PT
- The number and percentage of subjects with at least one AESI recorded by SOC and PT.

Unless otherwise stated, AEs will be displayed with SOC terms and PTs within each SOC term sorted alphabetically.

For determining incidence counts, within each level of TEAE term, if a subject experiences more than one occurrence, the subject will only be counted once for that TEAE.

If an AE is reported for a given subject more than once during treatment, the worst severity and the worst relationship to study treatment will be tabulated.

Adverse events related to IMP are those events with relationship missing, unknown or yes.

In case a subject had events with missing and non-missing severity, the maximum non-missing severity will be displayed.

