# 15.1.2 Adverse Events Leading to Study Discontinuation

A listing of TEAEs leading to study discontinuation, if any, will be provided.

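### In Part C, adverse events between malaria inoculation and M5717 that resolve or do not worsen are only listed, and a subject inoculated but never dosed is outside the Safety Analysis Set with no disposition row of its own

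*SAP*

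**What the plan says.** **Timing.** SAP section 12.3 places the inoculum at Day -8. Protocol section 5.2.4 gives an incubation period of 8 days, with M5717 planned for Inoculum Day 9, which is Trial Day 1.

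**Adverse event tables.** SAP section 15.1 counts an event as treatment-emergent if it starts on or after the first IMP dose. An earlier event that resolves before dosing, or does not worsen after it, "will be included in the AE listings, but will not be included in the summary tables (unless otherwise stated". Section 15.1.1 opens with "Treatment-emergent AEs will be summarized by dose and overall in tables with", and all its specifications follow from that sentence. Relationship is shown for the IMP only, for example "The number and percentage of subjects with at least one IMP-related TEAE by SOC and PT". Section 15.1.2 adds: "A listing of TEAEs leading to study discontinuation, if any, will be provided".

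**Population.** SAP section 8.2: "The Safety Analysis Set will include all subjects who receive investigational medicinal product (M5717 or placebo for Part A; M5717 for Part C". SAP section 15: "All safety analyses will be performed for the Safety Analysis Set and will be presented by part and dose".

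**Disposition.** The row in SAP section 10.1 for undosed subjects is "Number of randomized subjects who did not receive dose (as applicable". For Part C, Protocol section 6.3 says that "eligible subjects will receive the same M5717 dose with no need for randomization".

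**Routes to being inoculated but not dosed.** Protocol section 5.3 has eligibility checked again before IMP. Exclusion criterion 5b in section 5.3.2.1 applies a liver limit of 3 x ULN on Inoculum Day 8. Section 5.5.2 applies the liver withdrawal rules in Part C before IMP.

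**The concern.** Starting the count at the first IMP dose suits Part A, where no challenge precedes dosing. In Part C a deliberate infection comes first, and Protocol section 3.3.3 names malaria symptoms and transient liver enzyme rises as its risks. Part C has no placebo arm, so the days between inoculation and dosing are the only view within the trial of the challenge without M5717. Under the SAP, events confined to those days get no incidence, no worst-grade summary and no denominator.

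The subject stopped before dosing is the sharper case. Someone withdrawn because of the challenge is a subject whose safety outcome a reader would want to see counted, yet the safety denominators start only with those who went on to receive M5717. Protocol section 8.1 says that Part C subjects withdrawn for adverse events after inoculation will generally not be replaced. A cohort of 8 could then appear in the safety tables as 7.

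**Working it through.** The plan states no figure to reproduce. The check is mainly a comparison of rules, followed by arithmetic for scale.

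**1. Length of the window.** Inoculum Day 1 to Inoculum Day 9 is 9 - 1 = 8 days. With up to 24 subjects (Protocol synopsis), this is at most 24 x 8 = 192 subject-days. As a share of the time from inoculation to Day 44 it is 8 / (8 + 44) = 15%.

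**2. Tables that reach the window.** SAP section 15.1.1 has 7 specifications: overview, SOC/PT, worst grade, IMP-related, PT only, non-serious, and AESI. All stand under the treatment-emergent opening sentence, and section 15.1 makes treatment-emergent events the default. The AESI items do not repeat the term, but both of those rules govern them. No Part C exception is stated, so 0 of 7 cover events confined to the window. After dosing, event terms and worst grade are tabulated.

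**3. Tracing a never-dosed subject.** Suppose a subject reaches the Inoculum Day 8 liver limit and is not given M5717.
- Safety Analysis Set: not included, because M5717 was not received (SAP 8.2). All safety analyses use this set (SAP 15).
- Listing of events leading to discontinuation: not included, because the event precedes any IMP dose and so cannot be treatment-emergent (SAP 15.1, 15.1.2).
- Undosed disposition row: does not fit, because it counts randomized subjects and Part C has none (SAP 10.1, Protocol 6.3).
- Row for discontinuation before randomization: could be stretched to fit, but would mix this subject with screen failures.
- Enrolled Analysis Set, termination status and withdrawal-reason listings: included (SAP 8.2, 10.1). Counts for each analysis set are also summarized.
- Listings of SAEs and deaths (SAP 15.2.1, 15.2.2): worded without the treatment-emergent limit, but section 15 ties safety analyses to the Safety Analysis Set, so inclusion is uncertain.

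**4. Scale, on assumed rates.** The documents give neither a pre-dose event rate nor an undosed rate.
- Expected subjects with a listing-only event, 24 x q: q = 10%, 30% or 50% gives 2.4, 7.2 or 12.
- Chance of at least one undosed subject in 24, 1 - (1 - p)^24: p = 1%, 2% or 5% gives 21%, 38% or 71%.
- One such subject is 1/8 = 12.5% of a cohort and 1/24 = 4.2% of Part C.

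**The case against.** The strongest reply is that the SAP delivers what the protocol asks for. The Part C safety objective concerns M5717 in infected volunteers. Protocol section 8.5.2.1 sets the adverse event summaries by dose, relationship to IMP and severity, and section 8.5.3.2 has Part C analyzed similarly. Counting from the first dose is right for that purpose. With 8 subjects per cohort, a listing can be read in full. For dosed subjects, pre-dose laboratory values enter the summaries as the Day -1 baseline (SAP 9, 15.3), and the malaria clinical score is summarized (SAP 15.2.3). Liver elevations are AESIs reportable within 24 hours, and the SMC reviews liver derangements. Symptoms may also lead to earlier dosing rather than withdrawal. Protocol section 8.5.4 is blacked out and may say more.

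Most of this stands, and it limits the point to reporting. It does not supply a count or denominator for events confined to the window, or a place in the safety outputs for the never-dosed subject.

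Three stronger readings are tempting, and the documents do not support them:
- *M5717 event rates are wrong.* They are not: pre-dose events are properly left out of treatment-emergent rates.
- *A never-dosed subject disappears.* The subject stays in the Enrolled Analysis Set, with the withdrawal reason listed.
- *Inoculum-related events after dosing are hidden among those not related to the IMP.* No table shows relationship to the inoculum, but where such events fall depends on the eCRF. Protocol section 7.4.1.1 requires assessment against IMP or inoculum, and its definition of related also combines these with rescue medication. Section 7.4.1.2 names only IMP or rescue medication among the report items. Whether a separate inoculum field exists cannot be told.

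**Conclusion.** The point holds as a gap in reporting. A rule suited to Part A is applied to a part in which infection precedes the drug, so events confined to the pre-dose window appear only in listings. A foreseeable group, inoculated but never dosed, has no place in the safety denominators and no row of its own in disposition. No M5717 estimate changes, and no dose decision is shown to depend on this. Its size is unknown: the figures above illustrate assumed rates, and the 71% comes from the highest undosed rate assumed. The conclusion rests on the visible text and would weaken if the blacked-out safety section provided for this period. It is worth acting on because the remedy is small and adverse events are already collected from consent (Protocol 7.4.1.3).

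**What to change.** Amend the SAP only:
- Define a Part C Inoculated Set of all subjects who receive the inoculum.
- Add a Part C disposition row for subjects inoculated but not dosed, with the reason.
- Add one table and listing, on that set, of AEs and SAEs from inoculation to first M5717 (or to end of follow-up if never dosed), by SOC/PT and worst grade.
- Check whether the eCRF records relationship to the inoculum separately from relationship to the IMP. If it does, show it in the new table and in one row of the Part C treatment-emergent overview. If not, present the table by period alone.
- Leave the Safety Analysis Set and the existing treatment-emergent tables unchanged.

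The cost is one analysis set, one disposition row, one table with its listing and possibly one overview row, with no new data collection. The downside is an extra table that reports events not caused by M5717, so its title should make clear that it describes the challenge period.
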